7.1.1.1 Eligibility screening

While the investigator is responsible to ensure that each patient meets all inclusion/exclusion criteria prior to randomization, a subset of those criteria have been identified as key eligibility criteria and will also be verified by the sponsor through IRT prior to permitting the patient to be randomized. Patient's eligibility is checked in IRT. The eligibility checklist form must be completed in IRT by the investigator or designee at Day 1 prior to the patient starting the treatment phase and receiving the first dose of study drug (osilodrostat/placebo). Verification of all eligibility criteria must be done prior to contacting IRT. After the eligibility has been checked in IRT and confirmed that the patient is eligible for the trial, then the patient can be enrolled into the treatment phase of the study.

Please refer to and comply with detailed guidelines in the IRT manual.

7.1.1.2 Information to be collected on screening failures

Patients who sign an informed consent but fail to be started on treatment for any reason will be considered a screen failure. The reason for not being started on treatment will be entered on the Screening Phase Disposition Page.

The demographic information, informed consent and Inclusion/Exclusion pages must also be completed for Screen Failure subjects.

No other data will be entered into the clinical database for patients who are screen failures, unless the patient experienced a Serious Adverse Event during the Screening Phase (see [Section 8.2](#) for SAE reporting details).

If the patient fails to be randomized, the IRT must be notified within 2 days of the screen fail that the patient was not randomized.

7.1.1.3 Patient demographics and other baseline characteristics

The following patient demographics and baseline characteristics will be collected on the eCRF:

- Demography including date of birth, sex, predominant race and ethnicity (where permitted).
- Height, weight and waist circumference (see [Section 7.2.2.3](#)).
- Medical history (e.g., important medical, surgical, and allergic conditions from the patient's medical history which could have an impact on the patient's evaluation) / current medical conditions (e.g., all relevant current medical conditions which are present at the time of signing informed consent). Ongoing medical conditions, symptoms and diseases which are recorded on the Medical History eCRF should include the toxicity grade when applicable.
- Information on the most recent prior medical therapy for CD will be collected and will include information on drug, dose, duration of therapy and outcomes provided such data are available.
- Where possible, diagnoses and not symptoms will be recorded. Cushing's disease history together with the medication/treatment used will be collected.
- Prior and concomitant medications.

All assessments to be completed and documented during screening and at baseline are detailed in [Table 7-1a](#).

Day 1 assessments / samples should be taken before the patient receives study drug as these values will be considered the baseline values for the study. Where multiple values are available for a parameter prior to study drug, the last value prior to the start of study drug will be considered the baseline value.

7.1.2 Run-in period

The screening period should be viewed as a “run-in” period in which the treatment of co-morbidities is optimized (see rescue medication plan in [Section 6.1.3](#)). For details of assessments, refer to [Section 7.1.1](#) and [Table 7-1a](#).

7.1.3 Treatment phase

Treatment phase is divided in 2 study periods plus an Extension phase as described in [Section 4.1](#). Patients must be seen for all visits on the designated day with a visit window of ± 3 days for all visits, except Week 1 (Day 1) where the window is +3 days. During Period 1 (Weeks 1 to 12), patients will attend the site 2 weeks after starting study medication, and then at Weeks 5, 8 and 12.

During Period 2 (Weeks 12 to 48), patients will attend the site for the Week 14 visit, then every 3 weeks until Week 32, and every 4 weeks from Week 32 to Week 48.

At Week 48, patients have the option to enter a 48-week open-label extension phase. Patients not entering the optional Extension phase will complete the study with a 30 day follow-up.

Patients currently enrolled in the optional Extension phase must end study participation within 4 weeks after Protocol Amendment 02 is approved at the site, or by Week 96 whichever occurs first. Refer to [Section 6.1.5](#) for details. If patients are benefitting from study treatment, they have the option to enter a separate long-term safety follow-up study or stop study treatment. Patients not entering the long-term safety follow-up study will complete the study with a 30 day follow-up.

During study treatment phases, patients will be instructed to:

- bring urine samples (collected as described in [Section 7.2.1.1](#)) to each study visit
- complete a patient diary collecting information on study drug, and urine and salivary collections. The diary will be reviewed at each site visit by site staff.

For details of assessments, please refer to [Table 7-1a](#), [Table 7-1b](#) and [Table 7-2](#) for the Core and Extension, respectively.

7.1.4 Discontinuation of Study drug

Patients may voluntarily discontinue from the study drug for any reason at any time. If a patient decides to discontinue from the study drug, the investigator should make a reasonable effort (e.g. telephone, e-mail, letter) to understand the primary reason for this decision while respecting the subjects rights and record this information in the patient’s chart and on the appropriate eCRF pages. Patients may be considered withdrawn if they state an intention to withdraw, fail to return for visits, or become lost to follow-up for any other reason.

In order to help retain patients in the placebo-controlled phase (Period 1, Weeks 1 - 12), rescue therapy for co-morbid conditions should be optimized before a decision is made to discontinue patients from study drug or from the study.

Patients who discontinue study drug should NOT be considered withdrawn from the study. For patients who discontinue treatment during Weeks 1 - 12, investigators should make reasonable efforts to follow patients and perform all assessments identified for all visits up to and including Week 12 as indicated in [Table 7-1a](#) (Post-treatment follow-up) and [Section 7.1.6](#), even if study drug has been discontinued and alternative cortisol-lowering therapy has been initiated. Patients discontinuing study drug at any time before Week 48 of the Core phase or during the optional Extension phase, should be scheduled for an End of Treatment (EOT) visit as soon as possible, at which time the assessments listed for the EOT visit will be performed ([Table 7-1a](#), [Table 7-1b](#) and [Table 7-2](#)), with the following exceptions:

- Patients discontinuing treatment prior to the Week 36 visit do not need to have an EOT DXA scan
- Patients discontinuing prior to the Week 14 visit or between the Week 26 and Week 36 visits do not need to have an EOT pituitary MRI (or CT) (i.e. scans are needed if patients discontinue within the 12 week period prior to the Week 26 and Week 48 visits).

The date and reason for stopping the study drug should be recorded in the eCRF. If a patient fails to return for the assessments for unknown reasons, reasonable efforts (e.g. telephone, email, letter) should be made to contact them as specified in [Section 7.1.7](#).

The investigator must discontinue study drug for a given patient if he/she believes that continuation would be detrimental to the patient's well-being. The investigator must also contact the IRT to register the patient's discontinuation from study drug.

Patients must discontinue study drug if any of the following occur:

- Emergence of the following adverse events:
- hypertension defined as office mean supine systolic BP > 180 mmHg or mean supine diastolic BP > 110 mmHg (confirmed and persistent*).
- Any of the following laboratory abnormalities (confirmed):
 - hyperkalemia (serum potassium > 6.0 mmol/L).
 - hypokalemia (serum potassium < 2.8 mmol/L).
- Any of the following laboratory abnormalities (confirmed and persistent*):
 - hyperkalemia (serum potassium > 5.5 mmol/L).
 - hypokalemia (serum potassium < 3.0 mmol/L).
 - hyponatremia (serum sodium < 130 mmol/L).
 - hyperglycemia (fasting plasma glucose \geq 15.0 mmol/L).

* Persistent is defined as unresolved with osilodrostat dose change or after adjustments to other concomitant medications targeting the co-morbidity in question.

- Abnormal liver function as described in [Table 6-2](#).
- Mean QTcF > 500 msec, if the QTc value is confirmed by a cardiologist (see [Section 7.2.2.7](#)).

- Mean QTcF > 480 msec, if the investigator determines it is no longer safe for the patient to continue in the study, based on ECGs, cardiac examination, and recommendation from a cardiologist (see [Section 7.2.2.7](#)).
- Mean increase in QTcF > 30 msec from the mean baseline value at 1.5h post-first dose or the QTcF is > 480 msec at Day 1.
- QTcF increase > 60 msec from the pre-dose measurement earlier during the same visit.
- Pituitary tumor growth, if symptomatic or complicated by compression of the optic chiasm or other structures in and near the sella turcica (visual field loss, cranial nerve palsies, diplopia) and confirmed by MRI of the pituitary (see [Section 7.2.2.5](#)).
- Pregnancy.
- Use of prohibited treatment (refer to [Section 6.4.3](#)).
- Any other protocol deviation that results in a significant risk to the patient's safety.

The appropriate personnel from the site and Novartis will assess whether study drug should be discontinued for any patient whose treatment code has been broken inadvertently for any reason.

The investigator must also contact the IRT to register the patient's discontinuation from study drug within 2 days.

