2.2.6 ECG Monitoring

Cardiac monitoring will include 12-lead Safety ECGs at pre-dose (Day 1) and 1.5 hours post-dose at each visit the patient receives study drug. The Safety ECGs are the primary cardiac safety assessment, and their rationale is to assess the maximum change in QTcF in each individual patient each time they receive study drug at the site. The 12-lead safety ECGs are read in real-time on-site by the PI or other qualified physician (e.g., cardiologist), and if there is QT prolongation (QTcF > 480 ms or increase > 60 ms from baseline assessment), patients are to be managed according to the QT Monitoring Flow Chart in [Figure 7-2](#).

In addition, 24-hour continuous 12-lead Holter recordings will be performed at baseline, Weeks 2, 12, 14, 36, and as applicable at Week 72 and at the end of treatment visit in the optional Extension phase. The 24 hour Holter assessments are not intended to provide real-time assessment of cardiac intervals and cardiac rhythm; the recordings are read centrally.

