
*Patients will have only one ECG at Week 48 (Day 337). For patients not continuing in optional extension, ECG will be performed anytime during the visit. For patients continuing in optional extension, ECG will be performed at 1.5 hours post-dose, except for EOT Ext., if applicable
 
**For patients who discontinued study drug during Period 1.
 
***The patients who have completed Week 96 prior to the completion of study will be followed every six months as per the schedule of assessments in Table 7-2 until transitioning either to a separate long-term safety follow-up study, a local alternative treatment option, or the completion of the study, whichever occurs first.
 
****End of treatment optional Extension visit assessment should be completed at the time the patients are transitioning either to a separate long-term safety follow-up study, a local alternative treatment option, or the completion of the study, whichever occurs first. Note: Patients end participation in the optional extension period study within 4 weeks after Protocol Amendment 02 approval at the site, or by Week 96, whichever occurs first.
				

7.2.2.6.1 24-hour Holter Electrocardiogram

Twenty-four hour continuous 12-lead Holter recording with central reading of data are done on each patient according to the [Table 7-1a](#), [Table 7-1b](#), [Table 7-2](#), and [Table 7-6](#). Patients should be instructed to return their 24-hour Holter flashcards to the site at their next study visit in order to facilitate timely central reading of the Holter data.

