7.2.2.6.2 Electrocardiogram (ECG)

Twelve-lead safety ECGs are collected at the study sites according to [Table 7-1a](#), [Table 7-1b](#), [Table 7-2](#), and [Table 7-6](#). At each visit when a study drug dose is administered, the safety ECG should be collected at 1.5 hours post-dose (approximately at the time of C_{max}).

Twelve-lead safety ECGs are collected at the study site using ECG equipment provided by or validated by vendor. This ECG must be read on site by a qualified physician (e.g., the investigator, or another qualified physician such as a consulting cardiologist) at the time they are collected and documented on the ECG eCRF.

Each 12-lead Safety ECG tracing must be labeled with the:

- study number
- patient initials
- patient number
- date and time

and kept in the source documents at the study site. The clock on the ECG machine must be synchronized with the central clock on a daily basis.

Record the following on the eCRF:

- date and time of ECG
- heart rate
- PR interval
- QT and QTcF interval
- QRS duration

The Fridericia QT formula (QTcF) to correct for variations in heart rate must be used for clinical decisions.

The purpose of the safety ECG is to identify patients with clinically significant ECG abnormalities. On the day of the first study drug administration (Day 1), pre-dose ECGs must be done in triplicate. The mean of the QTcF from these 3 tracings is used as the baseline QTcF to be compared with subsequent ECGs.

ECGs with clinically significant abnormalities must be reported on the ECG eCRF. The overall interpretation will be collected with a Yes/No statement to confirm if any clinically significant abnormalities are present which need to be specified further.

A “notable ECG abnormality” is defined as:

- Day 1 only: an increase in QTcF > 30 msec at 1.5 hours post-dose, compared to the mean pre-dose baseline QTcF from the same day
- QTcF > 480 msec with acute cardiovascular risk, as assessed by a consulting cardiologist
- Any QTcF > 500 msec, confirmed by a consulting cardiologist
- QTcF increase > 60 msec from baseline.

Notable ECG abnormalities must be recorded on the Adverse Events eCRF page. If there is a notable abnormality, then a cardiology consult should be obtained as soon as possible, and the Novartis Medical Monitor for this trial notified of the event.

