For any ECGs with clinically significant or notable ECG abnormalities, two additional 12-lead ECGs should be performed to confirm the safety finding and the triplicate ECGs collected should be transferred for central review.

ECGs must be recorded after 10 minutes rest in the supine position to ensure a stable assessment.

The preferred sequence of cardiovascular data collection during study visits is ECG collection first, followed by vital signs, and then blood sampling for osilodrostat pharmacokinetic (PK) assessment (Figure 7-1). ECG procedure may also be performed 30 minutes after PK sampling.

Figure 7-1 Sequence of cardiovascular data collection

Original ECG tracings, appropriately signed, will be archived at study site.

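### Two mandatory stops in Protocol 7.1.4 do not fit the rest of the protocol: a >60 ms QTcF stop whose comparator is a safety ECG scheduled only on Day 1, and a prohibited-drug stop that catches eplerenone use allowed elsewhere

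*Protocol*

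**What the plan says.** **QTcF.** Section 7.1.4 lists events after which study drug must be stopped. One is a "QTcF increase > 60 msec from the pre-dose measurement earlier during the same visit". Another, for Day 1, is a mean rise above 30 ms over the mean baseline at 1.5 h after the first dose, or QTcF above 480 ms.

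The ECG schedule is in Section 2.2.6: "Cardiac monitoring will include 12-lead Safety ECGs at pre-dose (Day 1) and 1.5 hours post-dose at each visit the patient receives study drug". Table 7-6 agrees, and its footnote limits Week 48 to a single ECG. Table 7-6 also starts 24-hour Holters before the dose at Weeks 2, 12, 14, 36 and 72. Sections 2.2.6 and 7.2.2.6 say that Holters are not for real-time assessment.

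For later visits the comparator is the Day 1 triplicate. Section 7.2.2.6.2 says: "The mean of the QTcF from these 3 tracings is used as the baseline QTcF to be compared with subsequent ECGs". Section 7.2.2.7 and SAP 2.8.4.1 also measure a >60 ms rise from baseline. Under 7.2.2.7 a mean rise above 60 ms leads to interruption and an urgent cardiology consult. The outcome list that follows then requires nothing more if a mean above 480 ms is not confirmed.

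**Eplerenone.** Another mandatory stop in 7.1.4 is "Use of prohibited treatment", which points to Section 6.4.3. That section prohibits eplerenone except after myocardial infarction, or for refractory hypokalemia in a patient with hypertension or edema. Section 6.4.1 permits it to treat or prevent drug-related edema or hypokalemia. Table 6-1 suggests considering it to prevent and treat hypokalemia.

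**The concern.** A mandatory safety stop should be one that sites can apply, and apply alike. After Day 1 the >60 ms stop depends on a tracing that the schedule does not call for, so it operates only where a site happens to take one.

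Some text could prompt that. Section 6.1.1 has the visit-day dose follow the ECG, and 7.2.2.6.2 says "The preferred sequence of cardiovascular data collection during study visits is ECG collection first", with vital signs and PK sampling after it. The likeliest visits are Weeks 32, 36, 40 and 44, where Table 7-7 has only a pre-dose PK sample. Table 7-6 still puts the ECG at 1.5 h post-dose at those visits.

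For eplerenone, two sites giving the same treatment can act in opposite ways. One follows Table 6-1 and continues study drug; the other follows 6.4.3 and 7.1.4 and stops it. The situation is foreseeable. Hypokalemia is an anticipated effect of the drug and a listed QT risk factor, and confirmed and persistent potassium below 3.0 mmol/L is itself a mandatory stop.

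**Working it through.** The plan gives no figure to reproduce here, so the check is a count and a comparison of sections.

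**Step 1. Visits without the comparator (Table 7-6).**
- Core visits with a 1.5 h post-dose 12-lead ECG: Weeks 1, 2, 5, 8, 12, 14, 17, 20, 23, 26, 29, 32, 36, 40, 44 = 15. Removing Day 1 leaves 15 − 1 = 14.
- Dated extension visits with a post-dose ECG: Days 337, 421, 505, 589 = 4. Week 96 is not counted, because the SAP visit tables make Day 673 the end-of-treatment extension visit.
- Total after Day 1: 14 + 4 = 18. None has a scheduled pre-dose 12-lead safety ECG.
- Of these 18, a Holter starts before the dose at Weeks 2, 12, 14 and 36 (core) and Week 72 (Day 505) = 5. That leaves 18 − 5 = 13 with no scheduled pre-dose recording of any kind: 10 core and 3 extension.

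The five Holters are 12-lead and start before the dose, so a pre-dose recording does exist at those visits. It is read centrally and later, so it cannot drive a stop on site.

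**Step 2. Day 1.** A same-day rise above 60 ms is also above 30 ms. The >30 ms stop therefore covers it, and the >60 ms stop adds nothing.

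**Step 3. The 7.2.2.7 branch.** Let B be baseline QTcF and Q the later mean. The gap needs Q − B > 60 and Q ≤ 480, so B < 480 − 60 = 420 ms. Example: B = 405 and Q = 470 give a rise of 65 ms. That rise requires interruption, yet because 480 ms is not exceeded the text asks for no further action. Baselines below 420 ms are eligible, since exclusion starts above 450 ms (men) and 460 ms (women).

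**Step 4. Eplerenone.**

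| Use | 6.4.1 | Table 6-1 | 6.4.3, hence 7.1.4 |
|---|---|---|---|
| Prevention of hypokalemia | permitted | suggested | prohibited, stop |
| Non-refractory hypokalemia | permitted | suggested | prohibited, stop |
| Refractory hypokalemia, no hypertension or edema | permitted | suggested | prohibited, stop |
| Edema without refractory hypokalemia | permitted | not suggested | prohibited, stop |
| Refractory hypokalemia with hypertension or edema | permitted | suggested | allowed |
| Post-infarction | permitted | not addressed | allowed |

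The 6.4.1 permission for edema and hypokalemia is for drug-related cases. The conflict is in the first four rows.

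**Step 5. Upper bound on efficacy.** At the planned sizes (46 osilodrostat, 69 in all), one patient whose status turns on the eplerenone conflict moves the Week 12 osilodrostat rate by at most 1/46 = 2.2 points and the Week 36 combined rate by at most 1/69 = 1.4 points. The Clopper-Pearson 95% lower bound is 0.289 at 28/69, 0.302 at 29/69 and 0.469 at 41/69. Success against the 30% threshold therefore needs 29 responders. The planned 60% gives about 41 (0.60 × 69 = 41.4), a margin of 41 − 29 = 12.

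**The case against.** **Existing cover is substantial.** This stands. A >60 ms rise from baseline is a notable abnormality and must be recorded as an adverse event. Section 7.2.2.6.2 adds: "If there is a notable abnormality, then a cardiology consult should be obtained as soon as possible". The Medical Monitor is notified, and "two additional 12-lead ECGs should be performed to confirm the safety finding and the triplicate ECGs collected should be transferred for central review". The >480 ms, >500 ms and Day 1 rules work as written, and the investigator must stop drug whenever continuing would be detrimental. A reader might infer that patients have no QT protection after Day 1. The documents do not support that.

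**Holters supply a pre-dose 12-lead recording at five visits.** Correct, so the point must be limited to locally read safety ECGs. Within that limit it stands.

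**Section 7.2.2.7 describes a sequence: interrupt, consult, decide.** Largely fair. The no-action sentence comes after cardiology review, so the text is incomplete for this case and does not abandon the patient. Figures 7-1 and 7-2 are not shown, and Figure 7-2 may supply the missing outcome.

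**A reader might also infer a conflict within SAP 2.2.3**, because prohibited medication before Week 12 does not exclude a patient from the primary per-protocol set, while meeting a discontinuation criterion without being discontinued does. There is none. Any one listed item excludes a patient. The limit on the prohibited-medication item applies to that item alone, and it still has a use for a patient who took such a drug and was then discontinued. No rule of precedence is needed.

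**Little of the trial remained.** Also true. At Amendment 2 (20 December 2019) the last patient was due to finish Week 48 by the end of February 2020, about 10 weeks later, so on that schedule everyone was at roughly Week 38 or beyond. The Week 12 endpoint was past. On 10 December, 45 patients were on treatment: 10 in the core phase and 35 in an extension ending within 4 weeks of local approval.

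**Conclusion.** Both conflicts are in the current protocol text and should be corrected. After Day 1 the >60 ms stop has no scheduled on-site comparator at any of the 18 counted visits. The text of 7.2.2.7 leaves a confirmed >60 ms rise at or below 480 ms, possible only with a baseline under 420 ms, without a proper outcome unless Figure 7-2 provides one. Four kinds of eplerenone use are permitted in one place and a mandatory stop in another.

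The size is minor. The documents give no frequency for eplerenone use and no usable one for QTcF rises in these patients; the thorough QT study in healthy volunteers saw no rise above 60 ms. A reader might infer that the efficacy results are in doubt, because a patient stopped before Week 12 counts as a non-responder. The documents do not support that. The per-patient effect is bounded at 2.2 and 1.4 points, and the Week 36 conclusion has a margin of 12 responders at the planned rate. These bounds assume the planned sample sizes and the 60% planning rate. The case for change is patient safety and uniform conduct.

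**What to change.** **Section 7.1.4.** Keep the >60 ms stop at any visit where a same-visit pre-dose ECG was taken. Otherwise refer a mean rise above 60 ms over the Day 1 triplicate baseline to Section 7.2.2.7.

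**Section 7.2.2.7.** Reword the no-action branch to: *If neither a mean QTcF > 480 msec nor a mean increase > 60 msec is confirmed*. Send a confirmed >60 ms rise through the acute-risk assessment already used for >480 ms. Check Figures 7-1 and 7-2 against the result.

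**Section 6.1.1, if edited.** State that after Day 1 the safety ECG is at 1.5 h post-dose, with PK sampling and any scheduled Holter start before the dose. Do not say that only the PK sample precedes dosing, because that would contradict Table 7-6.

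**Eplerenone.** Use one definition in 6.4.1, Table 6-1 and 6.4.3. One option is to extend the 6.4.3 exceptions to the uses in 6.4.1 and Table 6-1, keeping the ban on use with ACE inhibitors. The choice needs medical sign-off.

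SAP 2.2.3 needs no change.

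**Cost.** Wording and a site memo, with no new visits, ECGs or samples. The changes do need a protocol amendment with the approvals in Section 12.1, and medical sign-off for the 7.2.2.7 route.
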